The Loneliness Epidemic Tailoring Interventions to Reduce Loneliness and Pain

NCT05387447

08-21-2023

Protocol

Setting and Recruitment

We will recruit participants: 1) direct referral from those with ethical access in independent or assisted and independent living facilities and 2) community and social media marketing. A copy of a letter of support will be uploaded from each senior retirement apartment. We will host informational sessions (PI, Co-Is, and study personnel) with question-and-answer periods at the facilities (in Omaha and Lincoln) to inform participants about the study. We will obtain permission from these facilities prior to placing flyers at any locations in the community and hosting study informational presentations. Interested individuals will undergo screening and enrollment.

The sites where the study will be conducted are the *participant's place of residence at the following locations*: Aksarben Village Senior Apartments Trinity Courtyard Senior Apartments (both in Omaha, NE) Eastmont Senior Living Apartments and The Legacy Senior Living (all in Lincoln, NE).

Screening

Study personnel (Omaha and Lincoln) will screen interested potential subjects according to inclusion and exclusion criteria in the private residence. Those meeting eligibility will undergo informed consent.

Inclusion: 1) men and women 60 years of age; 2) live alone (single-family home, independent, or assisted living); 3) self-report have experienced or currently experiencing musculoskeletal pain; and 4) wireless internet access via a broadband Internet connection.

Exclusion: 1) memory loss as evidenced by poor performance on the Mini Cog; 2) inability to speak English; 3) prior study participation; 4) prior use or current use of a conversational voice assistant; and 5) not willing to engage with the voice assistant.

Both UNMC and UNL personnel will conduct screening, enrollment, Alexa set-up with instructions and training, data collection, data analysis and interpretation.

Enrollment and Randomization

Once all participants are recruited and enrolled, participants will be randomly assigned with equal distribution to the conversational voice assistant-standard group (CVA-S) or the conversational voice assistant-enhanced loneliness routine treatment group (CVA-E). The study will be a 12-week randomized pilot trial.

Study Groups

Group 1. Conversational Voice Assistant Standard Loneliness Routine (CVA-S) Participants in the CVA-S group will receive an a priori set of evidence-based interactions to perform with the conversational voice assistant. The interaction dose will be 15 minutes performed once in the morning and once in the evening, at pre-set times. The participants will 1) do a meditation activity, 2) play an interactive trivia game, and 3) ask the assistant to tell a joke.

Group 2. Conversational Voice Assistant Enhanced Loneliness Routine (CVA-ELR) Participants in the CVA-ELR group will receive personalized intervention activities based on individual preferences and personality. The interaction dose will be 15 minutes performed once in the morning and once in the evening, at pre-set times and as needed. After collection of post-intervention data, participants will be compensated for their time.

Procedures

An appointment will be scheduled to set up Alexa, review instructions, and perform data collection by study personnel (Omaha and Lincoln). The instructions for both groups will include basic training by study personnel (Omaha and Lincoln) on how to use the conversational voice assistant. Then review of the loneliness routine based on group assignment. Data will be collected at pre (baseline) and post intervention (after 12-weeks).

Data

Pain Severity and Pain Interference: Subjective pain will be measured using the Brief Pain Inventory Short form (BPI-SF). The instrument has nine questions that measure pain severity and pain interference with function. The severity questions assess pain numerically ranging from 0 no pain to 10 pain as bad as you can imagine; interference questions assess interference from 0 no interference to 10 completely interferes. Higher scores indicate higher severity or interference with 0 being none, 1-3 mild, 4-6 moderate, 7-10 severe. The BPI-SF has Cronbach alphas ranging from 0.86-0.96.

Loneliness: Subjective social isolation and loneliness will be measured using the University of California Los Angeles, UCLA Loneliness Scale Version 3, a 20-item instrument with responses of never, rarely, sometimes, and always. There is no standard accepted score for identifying loneliness; higher scores reflect greater reported loneliness. The scale has established validity and reliability with Cronbach's alphas ranging from 0.85 to 0.94.

Depression: Will be measured as it may interfere with pain and loneliness. We will use the Geriatric Depression Scale Short form. The instrument has 15 questions with higher scored indicating depression.

Self-management of Pain: PROMIS Self-Efficacy for Managing Symptoms-SF-8: an eight-item tool that allows the subjects to report the level of confidence to manage/control their symptoms, to manage their symptoms in different settings (home, public place, an unfamiliar place), and to keep their symptoms from interfering with work, sleep, relationships, or recreational activities.

Objective Use: We will securely access the participants voice assistant profiles and document the time stamps of intervention activities to assess frequency and length of use, type of uses, and routine completion rates with the standard and enhanced loneliness routines.

Usability: Usability will be measured using the System Usability Scale. The 10 question 5-point Likert scale scores range from 0-100 and scores above 68 are above average.

Personality Inventory: The Big Five Inventory is a 40-item assessment of general personality using the five-factor model Neuroticism (N), Extraversion (E), Openness to Experience (O), Agreeableness (A), and Conscientiousness (C).

Statistical Analysis

Descriptive statistics to calculate inferential results such as percentages, mean and standard deviations on demographic, health history, BPI-SF, UCLA Loneliness Scale, Geriatric Depression, and PROMIS Self-efficacy scores at baseline and after the 12-week intervention.

We will compare the average questionnaire scores within and between the CVA-S and CVA-E groups. The Shapiro-Wilk test used to assess the normality of distributions for these variables. Given the significant results, indicating non-normal distributions from the Shapiro-Wilk test for these variables except baseline pain severity and post-study severity, Wilcoxon Signed-Rank non-parametric test was chosen for hypothesis testing of all variables except baseline pain severity and post-study severity, which were tested by paired-samples t-test. In addition, ANOVA tests were performed to compare the baseline scores of self-reported pain severity, pain interference, loneliness, depression, and self-efficacy between the CVA-S and the CVA-E groups.

Mann-Whitney U test was employed to test differences between the standard and enhanced conditions in terms of routine initiation rates and SUS scores. Multiple regression analyses were conducted to explore the relationships between participants' SUS scores, objective use of the routines with personality.

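### The only tests named for change in the questionnaire scores are paired pre-post tests, which cannot show a device effect because no participant is left untreated

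*Combined protocol and SAP*

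**What the plan says.** Under Enrollment and Randomization, the plan says "Once all participants are recruited and enrolled, participants will be randomly assigned with equal distribution to the conversational voice assistant-standard group (CVA-S") or to the enhanced group, and "The study will be a 12-week randomized pilot trial".

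Under Study Groups, both arms use the device. For the standard arm, "Participants in the CVA-S group will receive an a priori set of evidence-based interactions to perform with the conversational voice assistant". For the enhanced arm, "Participants in the CVA-ELR group will receive personalized intervention activities based on individual preferences and personality". Under Procedures, "The instructions for both groups will include basic training by study personnel (Omaha and Lincoln) on how to use the conversational voice assistant". No untreated or attention-only group is described.

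Procedures also fixes the measurement times: "Data will be collected at pre (baseline) and post intervention (after 12-weeks"). Data collection is part of the same appointment as device set-up.

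Under Statistical Analysis, questionnaire scores are to be compared both inside each group and across the two groups. The tests then named are:

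- "Wilcoxon Signed-Rank non-parametric test was chosen for hypothesis testing of all variables except baseline pain severity and post-study severity", with a paired t-test for pain severity;
- ANOVA between arms, on baseline scores only;
- Mann-Whitney between arms, on routine initiation rates and System Usability Scale scores only.

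No between-arm test is named for loneliness, pain, depression or self-efficacy after baseline.

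**The concern.** The title sets the aim of reducing loneliness and pain. The tests that speak to that aim are the paired ones, and a significant paired result invites the reading that the voice assistant worked. Several other things can move the scores over 12 weeks:

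- Musculoskeletal pain fluctuates.
- People may volunteer when they feel worse than usual, so later scores drift back.
- The 12 weeks fall in a particular season.
- People who live alone receive home visits and training from study staff.

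None of these can be separated from the device when everyone has it. Randomisation removes what the arms share, but only from a comparison between arms, and the plan names no such test for these outcomes after baseline. Nor does it say how a within-arm change may be described.

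**Working it through.** **No figure to reproduce.** The documents state no sample size, significance level, standard deviation, correlation or expected effect. Everything below rests on assumed inputs and shows only how sensitive the named tests are to a change that the device did not cause.

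**1. What each comparison estimates.** Let d be the 12-week change common to both arms (natural course, regression to the mean, season, shared attention), and let τS and τE be the effects of the standard and enhanced routines.

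- Within the standard arm: expected change = d + τS.
- Within the enhanced arm: expected change = d + τE.
- Between arms: (d + τE) − (d + τS) = τE − τS.

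A paired test asks whether d + τ is zero, and no measurement in the plan identifies d. The between-arm difference is free of d.

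**2. Paired t-test, drift in baseline SD units.** Assume equal SDs at both times, pre-post correlation r, n per arm, two-sided 5%, and τ = 0. The SD of the change is √(2(1 − r)) baseline SDs, so the standardised drift is dz = drift/√(2(1 − r)). The rejection probability comes from the noncentral t with n − 1 degrees of freedom and noncentrality dz·√n.

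For r = 0.7, √(2 × 0.3) = 0.775. With n = 20:

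| Drift (baseline SD) | dz | Probability of significance |
|---|---|---|
| 0 | 0 | 0.05 |
| 0.2 | 0.258 | 0.20 |
| 0.3 | 0.387 | 0.38 |
| 0.4 | 0.516 | 0.59 |

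For a 0.3 SD drift, the range over r = 0.6 to 0.8 and n = 15 to 30 runs from 0.23 (r = 0.6, n = 15) to 0.71 (r = 0.8, n = 30).

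**3. Wilcoxon and between-arm tests.** Here drift is in units of the SD of the change, so the figures are not directly comparable with step 2. The paired t column is exact; the other two are simulated under normal changes with no device effect.

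| n per arm | Drift (SD of change) | Paired t | Wilcoxon signed-rank | Between-arm t on change |
|---|---|---|---|---|
| 15 | 0.3 | 0.19 | 0.18 | 0.05 |
| 20 | 0.3 | 0.25 | 0.24 | 0.05 |
| 30 | 0.3 | 0.36 | 0.35 | 0.05 |
| 15 | 0.5 | 0.44 | 0.42 | 0.05 |
| 20 | 0.5 | 0.57 | 0.55 | 0.05 |
| 30 | 0.5 | 0.75 | 0.74 | 0.05 |

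Using the Wilcoxon test in place of the t-test does not help. The between-arm test holds its level in every row.

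**4. Could the wait before allocation serve as a control?** Suppose scores were also taken at enrolment, L weeks before set-up, and the wait-period change were scaled to 12 weeks with k = 12/L. The contrast is post − (1 + k)·baseline + k·enrolment. With equal correlations its variance is (1 − r)(1 + (1 + k)² + k²), against 2(1 − r) for simple pre-post change. Power is for a true 0.5 SD device effect at n = 20 and r = 0.7.

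| Wait | k | Variance ratio | Power |
|---|---|---|---|
| Simple pre-post, no wait used | – | 1 | 0.78 |
| 12 weeks | 1 | 6/2 = 3 | 0.35 |
| 4 weeks | 3 | 26/2 = 13 | 0.12 |
| 1 week | 12 | 314/2 = 157 | 0.06 |

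A formal test against a scaled wait-period change loses most of its power even at 12 weeks.

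**The case against.** The strongest defence is that the trial asks whether tailoring helps. The title speaks of tailoring, the randomised contrast is standard versus enhanced, and an active comparator suits that question. The plan says that scores will be compared across groups as well as inside them, it calls the study a pilot, and no sentence attributes within-arm change to the device. The drift values above are also assumed.

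Much of this stands. The active comparator is not itself an error, and the misreading is a risk rather than something the plan commits to. But the general statement about comparing groups is not carried into a named test of questionnaire scores after baseline, while the paired tests are named as the hypothesis tests. The assumed drift affects the size of the problem, not its existence.

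Two stronger readings are tempting. A reader might infer that late randomisation is the cause, because it forces everyone into the same season. The documents do not support that. Set-up is by individual appointment in two cities, so a common start is not established, and the paired tests would be uncontrolled whenever allocation took place. The cause is the missing untreated comparator.

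A reader might also infer that the wait between enrolment and allocation is a ready-made untreated control. A wait is implied for those enrolled early, but its length is not stated and nothing is measured in it. It falls at a different time of year from treatment and lacks the set-up contact. It is close to nil for the last enrolled. If people enrol when they feel worse, most of the regression to the mean would fall inside it, so subtracting it could hide a real effect.

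**Conclusion.** The concern holds in a limited form. As named, the tests of change in loneliness, pain, depression and self-efficacy cannot distinguish a device effect from change that would have happened anyway. Under the assumptions of 20 per arm and correlation 0.7, a drift of 0.2 to 0.4 baseline SD raises the chance of a significant paired t-test from 0.05 to between 0.20 and 0.59. These values illustrate sensitivity and do not estimate the drift in this trial. The calculation treats the paired tests as run within each arm. The text does not say whether they are pooled; pooling would enlarge n and raise these probabilities.

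The randomised enhanced-versus-standard comparison is sound against shared drift. It answers whether personalisation adds anything, not whether either routine works. The weakness lies in which test carries the conclusion, and it can be corrected in the analysis text.

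**What to change.** In Statistical Analysis:

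1. State that the paired Wilcoxon and t-test results describe change over time and will not be attributed to the device.
2. Name a between-arm test of 12-week change for each questionnaire outcome, and base efficacy conclusions on that randomised difference. This completes the across-group comparison that the section already announces.

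The cost is a few sentences and more modest within-arm claims. The between-arm test will not be powerful in a small pilot. By the normal approximation Φ(0.5·√(n/2) − 1.96), power for a difference of 0.5 SD of the change is 28%, 35% or 49% at an assumed 15, 20 or 30 per arm, so the estimate and its confidence interval should lead.

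Optionally, if recruitment is still open, also give the UCLA Loneliness Scale and BPI-SF at enrolment and record the dates. Report any change before set-up descriptively, as a partial check on drift, without scaling by interval length and without a formal test against the device period. This adds two short questionnaires at an existing contact. It does not control for season or set-up contact and tells nothing about late enrollees. The analysis text is partly in the past tense and reports normality results, so this option may already have passed; the wording changes remain available.

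### Depression is measured as a factor that may interfere with pain and loneliness, but no planned analysis of either outcome takes it into account

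*Combined protocol and SAP*

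**What the plan says.** In the Data section, the Depression paragraph gives one reason for collecting the scale: "Depression: Will be measured as it may interfere with pain and loneliness". The instrument is named next: "We will use the Geriatric Depression Scale Short form". Under Procedures, data are collected at baseline and after 12 weeks, so a baseline score will exist.

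The Statistical Analysis section uses the score in three ways:

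- Descriptive summaries, in a list that ends with "Geriatric Depression, and PROMIS Self-efficacy scores at baseline and after the 12-week intervention".
- The general questionnaire comparison: "We will compare the average questionnaire scores within and between the CVA-S and CVA-E groups". The only test named that covers depression here is a paired one: "Wilcoxon Signed-Rank non-parametric test was chosen for hypothesis testing of all variables except baseline pain severity and post-study severity".
- A baseline check: "ANOVA tests were performed to compare the baseline scores of self-reported pain severity, pain interference, loneliness, depression, and self-efficacy between the CVA-S and the CVA-E".

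The one multivariable analysis concerns other variables: "Multiple regression analyses were conducted to explore the relationships between participants' SUS scores, objective use of the routines with personality".

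Under Enrollment and Randomization, allocation is equal between two arms and no stratification factor is named. Depression is not among the exclusions listed under Screening.

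**The concern.** The plan identifies depression as something that could disturb its two target outcomes and collects it at the right time, but then keeps it out of every loneliness and pain result. The Wilcoxon signed-rank and paired t-tests named for those outcomes take no covariate. The baseline ANOVA covers five scores alike, and the plan does not say what follows from a significant or a non-significant result.

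If the arms happen to differ in baseline depression, part of an observed 12-week difference in loneliness or pain could reflect that difference. The team would hold the data needed to correct for it but would have no planned way to do so. Any outcome variance that depression explains would also stay in the error term.

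**Working it through.** **Trace of the depression score**

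| Stage | Role of depression |
|---|---|
| Eligibility (Screening) | None listed |
| Allocation (Enrollment and Randomization) | No stratification named |
| Descriptive statistics | Summarised at baseline and 12 weeks |
| Questionnaire comparison | Analysed as a score in its own right |
| Baseline ANOVA | One of five scores compared between arms |
| Loneliness and pain tests | Absent |
| Multiple regression | Absent (usability, routine use, personality) |

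The rationale therefore has no matching analysis of loneliness or pain.

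**Size.** The documents give no sample size, standard deviation or correlation, so there is no stated figure to reproduce. The inputs below are assumptions: n = 15, 20 or 30 per arm, and a partial correlation r of 0.2 to 0.4 between baseline depression and the 12-week outcome, given the baseline outcome.

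*1. Chance imbalance.* In SD units, the baseline difference between arms has standard error √(2/n). So P(|difference| > x) = 2Φ(−x/√(2/n)). At n = 20, √(2/20) = 0.316. For x = 0.3, 2Φ(−0.95) = 34%. For x = 0.4, 2Φ(−1.26) = 21%.

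| n per arm | Above 0.3 SD | Above 0.4 SD |
|---|---|---|
| 15 | 41% | 27% |
| 20 | 34% | 21% |
| 30 | 25% | 12% |

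*2. What the baseline ANOVA can detect.* An observed difference reaches two-sided p < 0.05 only beyond t × √(2/n). At n = 20 this is 2.02 × 0.316 ≈ 0.64 SD. It is about 0.75 SD at n = 15 and 0.52 SD at n = 30. Power against a true 0.5 SD difference is about 28%, 35% and 49% at n = 15, 20 and 30 (normal approximation). The imbalances in step 1 would pass as non-significant.

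*3. What an imbalance does to the outcome.* The shift in the arm difference is roughly r × imbalance, in residual SD of the outcome. With r = 0.3 and 0.3 SD it is 0.3 × 0.3 = 0.09. With r = 0.4 and 0.4 SD it is 0.4 × 0.4 = 0.16. The standard error of the arm difference at n = 20 is about 0.316 on the same scale, so the larger shift is 0.16/0.316 ≈ 0.5 of a standard error.

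*4. Precision.* Adding depression to a model that already has arm and baseline outcome changes the interval width by the factor √[(1 − r²)(N − 3)/(N − 4)]. At N = 40, (N − 3)/(N − 4) = 37/36 = 1.028.

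- r = 0.2: √(0.96 × 1.028) = 0.993, about 1% narrower
- r = 0.3: √(0.91 × 1.028) = 0.967, about 3% narrower
- r = 0.4: √(0.84 × 1.028) = 0.929, about 7% narrower

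**The case against.** The plan does not promise adjustment. It says only that depression is measured because it may interfere. Describing the score at both times and comparing it between arms at baseline is a weak but real response to that sentence. A reader might infer that depression is treated purely as one more outcome and that its purpose is never served. The baseline ANOVA is a balance check, so the text does not support that reading. What stands is narrower: the check triggers nothing and detects little in a small trial.

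A reader might also infer that the between-arm results are confounded by depression. Randomisation rules that out as a systematic effect. An unadjusted interval already allows for chance differences in depression, so leaving it out costs precision and leaves any particular imbalance uncorrected.

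Nor does an imbalance between arms undermine the signed-rank and paired t-tests. These compare scores before and after, and a difference between arms does not bias a within-arm change. A between-arm covariate would leave those tests as they are.

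Three further points limit the case. Every magnitude is assumed, and nothing in the documents favours a correlation of 0.3 to 0.4 over 0.2. The plan names no 12-week between-arm test for loneliness or pain, so depression would enter a model that first has to be specified. That model must also cope with scores the plan describes as non-normal. All of this stands. It makes the point modest but does not remove the mismatch between rationale and analysis.

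**Conclusion.** The point holds in limited form. Beyond descriptive summaries, its own score comparison and a baseline ANOVA without consequence, depression plays no part in the plan, and no loneliness or pain result accounts for it. The randomised comparison is not systematically biased.

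The loss is uncorrected chance imbalance, at most about half a standard error in the cases worked above, and a forgone gain in interval width of about 3% to 7%, falling to about 1% at a partial correlation of 0.2. These figures rest on an assumed 20 per arm and assumed correlations. The mismatch itself rests on the text alone. The change is worth making because the baseline score is already collected, but the trial's validity does not depend on it.

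**What to change.** For the 12-week enhanced-versus-standard comparison, specify a linear model (ANCOVA) for each of UCLA loneliness, BPI-SF severity and BPI-SF interference. The terms are arm, the baseline value of the outcome and the baseline Geriatric Depression Scale score. Use robust or bootstrap standard errors, or a rank-based ANCOVA, because the plan reports non-normal distributions for most scores.

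Do not adjust for the 12-week depression score, which the intervention may itself change. Do not rely on the baseline ANOVA as the safeguard against imbalance.

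The Statistical Analysis section describes its tests in the past tense and chooses them in the light of normality results. If outcome data have already been analysed, report this model as added post hoc, next to the unadjusted result, and do not call it pre-specified. If the team prefers not to adjust, it should withdraw the stated reason for measuring depression.

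The cost is the wording of a between-arm model, which the plan needs in any case, and one degree of freedom per covariate (40 − 4 = 36 residual degrees of freedom at an assumed 40 in total). No new data are required. If the correlation is low, there is little gain in precision.

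### The randomised comparison has no analysis: no named test compares the arms on 12-week loneliness, pain, depression or self-efficacy

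*Combined protocol and SAP*

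**What the plan says.** Enrollment and Randomization describes equal random allocation to the standard (CVA-S) or enhanced (CVA-E) routine and says "The study will be a 12-week randomized pilot trial". Procedures places data collection at baseline and after 12 weeks.

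Statistical Analysis opens its inferential part with a promise: "We will compare the average questionnaire scores within and between the CVA-S and CVA-E groups". It then names the tests:

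- "Wilcoxon Signed-Rank non-parametric test was chosen for hypothesis testing of all variables except baseline pain severity and post-study severity"; the two severity scores are the exception, "which were tested by paired-samples t-test".
- "ANOVA tests were performed to compare the baseline scores of self-reported pain severity, pain interference, loneliness, depression, and self-efficacy", between the two arms.
- "Mann-Whitney U test was employed to test differences between the standard and enhanced conditions in terms of routine initiation rates and SUS scores".
- Multiple regressions relating usability scores and objective use to personality.

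Means and standard deviations of the questionnaires are also planned at both time points. The section does not say that they will be tabulated by arm.

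**The concern.** The title concerns tailoring interventions to reduce loneliness and pain, and the design sets a tailored routine against a standard one. The quantity the randomisation supports is the CVA-E minus CVA-S difference after 12 weeks. The plan says it will compare the arms, but the only between-arm test it names for these scores looks at them before the routines begin.

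Both arms receive an active routine and there is no untreated arm. Pre-post change within an arm therefore mixes any effect of the routine with time, attention and regression to the mean. A reader given only paired p-values might conclude that tailoring works, or does not, without the arms having been compared. A later trial would also lack the between-arm estimate and interval that a pilot can supply.

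**Working it through.** The documents give no sample size, SD, effect size or pre-post correlation, so there is no design figure to reproduce. The check is of what each named test covers.

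**Step 1. Coverage of the five scores** (five scores from four instruments, because the BPI-SF yields both severity and interference)

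| Named test | Applied to | Contrast | Compares arms after treatment on the five scores? |
|---|---|---|---|
| Wilcoxon signed-rank | all except pain severity | pre versus post | No |
| Paired t-test | pain severity | pre versus post | No |
| ANOVA | all five | arms, at baseline | No |
| Mann-Whitney U | SUS, routine initiation | arms | No, other variables |
| Multiple regression | SUS, use, personality | association | No |

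Pre-post test: 5 of 5. Between-arm test at baseline: 5 of 5. Between-arm test at 12 weeks or on change: 0 of 5.

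**Step 2. What the named tests address.** Let δS and δE be the true changes in the two arms. A paired test takes one difference per person and asks whether its centre is zero. Run per arm, it tests δS = 0 and δE = 0 separately. Pooled with equal arms, it tests (δS + δE)/2 = 0. The text of the test sentence does not say which is meant, and neither is δE − δS. The baseline ANOVA compares arms before the routines are used, so it carries no information on either change.

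**Step 3. Per-arm tests as a substitute (illustration, assumed inputs).** If both arms change equally and each test has power p, the chance that exactly one is significant is 2p(1 − p):

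- p = 0.05: 2 × 0.05 × 0.95 = 9.5%
- p = 0.2: 2 × 0.2 × 0.8 = 32%
- p = 0.5: 2 × 0.5 × 0.5 = 50%
- p = 0.8: 2 × 0.8 × 0.2 = 32%
- p = 0.9: 2 × 0.9 × 0.1 = 18%

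Simulation with the exact signed-rank test, normal change scores and 8,000 trials per cell gives the share of trials with exactly one arm at p < 0.05:

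| Equal true change (SD of change) | 15 per arm | 20 per arm | 25 per arm |
|---|---|---|---|
| 0.3 | 0.292 | 0.361 | 0.413 |
| 0.5 | 0.477 | 0.494 | 0.453 |

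Over 10–40 per arm and changes of 0.3–0.7 SD the range is 0.023 to 0.501. With no change in either arm it is 0.092–0.100.

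**Step 4. Pooled tests (illustration).** The average change is held at 0.5 SD and split between the arms as 0.5/0.5, 0.9/0.1 or 0.1/0.9, with 6,000 trials. The pooled signed-rank test is significant in 0.741/0.695/0.669 (15 per arm), 0.864/0.816/0.810 (20) and 0.923/0.895/0.900 (25). A large arm difference in either direction barely changes the result.

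**Step 5. Whether a between-arm analysis would behave acceptably.** Assumptions: 15–25 per arm, pre-post correlation r of 0.5–0.8, normal and lognormal-skewed scores, equal change, 6,000 trials. False-positive rates were:

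- ANCOVA 0.041–0.053
- rank ANCOVA 0.046–0.055
- Mann-Whitney on change 0.044–0.051
- ANCOVA with HC3 robust errors 0.028–0.044, somewhat conservative

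The ANCOVA 95% half-width in SD of the score is about t × √(1 − r²) × √(2/n). With n = 15 and r = 0.5 (27 df): 2.05 × 0.866 × 0.365 = 0.65. With n = 25 and r = 0.8 (47 df): 2.01 × 0.6 × 0.283 = 0.34. The simulated mean range is 0.343–0.654. The simulated variance of ANCOVA was 0.73–0.95 of that for change scores and 0.37–0.81 of that for unadjusted 12-week scores.

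**The case against.** The strongest reply is that this is a pilot with no stated primary endpoint or efficacy hypothesis. The arms are compared on usability and routine initiation, which are typical pilot outcomes. The opening sentence announces the between-arm comparison, so the contrast is not ignored. If 12-week means and SDs were tabulated by arm, a reader could form an unadjusted difference and interval. Nothing in the plan says that the investigators will read significance in one arm only as an arm difference. Finally, ANCOVA and dropping baseline p-values are choices; any valid between-arm method would close the gap.

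Much of this stands as qualification. A pilot need not power the contrast, and the step 3 figures matter only if someone draws that inference. The opening sentence makes the per-arm reading of the paired tests more natural, so step 4 is secondary. The baseline ANOVA need not be removed in order to add a 12-week comparison.

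A point of timing also deserves care. Procedures does not settle whether baseline questionnaires are completed before participants know their arm, so it is not certain that randomisation alone makes the baseline null true. Data collection is nonetheless listed before the group-specific routine is reviewed, so a baseline comparison precedes treatment either way.

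None of this supplies the missing method. The pilot label did not prevent between-arm tests of usability and initiation, and significance tests are run on the five scores themselves.

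**Conclusion.** The concern holds and should be fixed. The plan announces a between-arm comparison of questionnaire scores, yet for the five scores that include the title outcomes it names no test, model or estimate that compares arms at 12 weeks or on change. That conclusion comes from the text and needs no assumption.

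The numerical consequences do rest on assumptions, because the documents give no n, SD, effect or correlation. If per-arm tests are read against each other, an apparent arm difference arises in about 29–49% of trials with equal true change of 0.3–0.5 SD and 15–25 per arm. If the tests are pooled, they are nearly blind to arm. These figures illustrate the risk and do not measure it in this trial.

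**What to change.** In Statistical Analysis, name a between-arm analysis for each of the five scores: the 12-week score regressed on arm and that score's baseline (ANCOVA). Given the reported non-normality, use bootstrap or robust standard errors or a rank-based equivalent; HC3 errors may be conservative at pilot sizes. Mann-Whitney U on change scores can serve as a sensitivity check; the plan already uses this test, though for other variables. Adjustment for baseline depression is optional.

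Report CVA-E minus CVA-S with a 95% confidence interval as a pilot estimate, not as five efficacy tests. Present baseline scores by arm descriptively, without p-values. State whether the pre-post tests are per arm or pooled, and treat them as descriptive. State whether baseline was recorded before participants knew their assignment. Because the section already reports Shapiro-Wilk results, label the between-arm analysis post hoc if outcome data have been examined.

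The cost is SAP wording and a re-analysis of scores already collected, with no new participants or visits. The downsides are an imprecise estimate, a result that may be less favourable than the pre-post p-values, and the post hoc label where it applies.
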